5.4. Tertiary endpoints

5.4.1. CMI response up to 1 month post-Dose 3

The following CMI responses will be computed as described in section 5.3.2.1:

- Frequency of RSVPreF3-specific CD8+ T-cells expressing **at least 2 markers** among IL-2, CD40L, TNF- α , IFN- γ , as measured by ICS using PBMCs.
- Frequency of RSVPreF3-specific CD4+ T-cells expressing **at least 2 markers including at least 1 cytokine*** among CD40L, 41BB, IL-2, TNF- α , IFN- γ , IL-13, and IL-17, as measured by ICS using PBMCs.
* *cytokines are IL-2, TNF- α , IFN- γ , IL-13, and IL-17*
- Frequency of RSVPreF3-specific CD4+ T-cells expressing **at least IFN- γ (Th1-like response)**, as measured by ICS using PBMCs.
- Frequency of RSVPreF3-specific CD4+ T-cells expressing **at least IL-13 (Th2-like response)**, as measured by ICS using PBMCs.
- Frequency of RSVPreF3-specific CD4+ T-cells expressing **at least IL-17 (Th17-like response)**, as measured by ICS using PBMCs.
- **Co-expression profile:** Frequency of RSVPreF3-specific CD4+ T-cells expressing **any combination of marker(s) among** CD40L, IL-2, TNF- α , IFN- γ , as measured by ICS using PBMCs, at Day 1 and Day 31 (\rightarrow 15 combinations).

5.5. Additional analyses Due to the Covid-19 Pandemic

A standardized MedDRA Query (SMQ) will be used to identify all COVID-19 AEs.

The overall incidence of COVID-19 AEs and SAEs, COVID-19 AEs leading to study intervention discontinuation, COVID-19 AEs leading to study withdrawal, and severe COVID-19 AEs will be summarized. The incidence of these events at individual PT level can be obtained from the standard AE/SAE summaries.

COVID-19 assessments (confirmed, probable and suspected diagnosis) for participants with COVID-19 AEs will be summarized.

The number and percentage of participants with concomitant vaccination (COVID-19) before and during the study will be tabulated with exact 95% CI.

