6.5. Concomitant therapy

At each study visit/contact, the investigator or delegate should question the participant about any medications/products taken and vaccinations received by the participant.

The following concomitant medication(s)/product(s)/vaccine(s) must be recorded in the eCRF:

- All concomitant medications/products/vaccines, except vitamins and dietary supplements, administered during the 30-day period following vaccination (Day 1 to Day 31).
- Any concomitant medications/products/vaccines leading to study participation/intervention non-eligibility, or an elimination from the analysis (refer to Section 5.2.2 for details).
- Any prophylactic medication (e.g. analgesics, antipyretics) administered on the day of study vaccination (Day 1) and in the absence of ANY symptom and in anticipation of a reaction to the vaccination.
- Any concomitant medications/products/vaccines relevant to an SAE/pIMD to be reported as per protocol or administered at any time during the study period for the treatment of an SAE/pIMD. Concomitant medications relevant to SAEs and pIMDs must be recorded on the Expedited Adverse Event Report.
- *Shingrix* or any AS01-containing vaccine throughout the entire study.

CONFIDENTIAL213569 (RSV OA=ADJ-011 EXT:002 MTH20)
Protocol Amendment 1 Final

The Local Medical Lead (LML) should be contacted if there are any questions regarding concomitant or prior therapy.

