10.3.7.1. Time period for collecting and recording AEs, SAEs, and pIMDs

All AEs that occur during 30 days following administration of the dose of study vaccine (Day 1 to Day 31) must be recorded into the appropriate section of the eCRF, irrespective of intensity or whether or not they are considered vaccination-related.

CONFIDENTIAL213569 (RSV OA=ADJ-011 EXT:002 MTH20)
Protocol Amendment 1 Final**10.3.7.2. Follow-up of AEs, SAEs, pIMDs**

After the initial AE/SAE/pIMD or any other event of interest for the study, the investigator is required to proactively follow each participant at subsequent visits/contacts. All SAEs and non-serious AEs of special interest as defined in the Section [10.3.5.1](#), will be followed until the event is resolved, stabilized, otherwise explained, or the participant is lost to follow-up.

Other non-serious AEs must be followed until 30 days after the last vaccination or until the participant is lost to follow-up.

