5.2.2.1.2. Unsolicited Adverse Events

For analysis of unsolicited AEs, SAEs, pIMDs and concomitant medications, all vaccinated participants will be considered. Participants who did not report an event or concomitant medication will be considered as participants without the event or the concomitant medication, respectively.

When an unsolicited adverse event occurs more than once for a participant, the maximal severity and strongest relationship to the vaccine group will be counted. The selection of unsolicited AEs reported during the follow-up period will be done using the day of onset.

Listing of AEs/SAEs leading premature withdrawal from study or to interruption of vaccination will be described in detail.

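### SAP 5.5 tabulates COVID-19 vaccination during the whole study, but Protocol 6.5 does not clearly require such vaccines to be recorded after Day 31, so the percentage is likely to be too low

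*SAP*

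**What the plan says.** SAP 5.5, dated 15 July 2021 in the SAP document history and written against Protocol Amendment 1 of 4 November 2020, plans this table: "The number and percentage of participants with concomitant vaccination (COVID-19) before and during the study will be tabulated with exact 95% CI". It gives no end day and no denominator. Protocol 4.1 puts participation at about 6 months, and Protocol Table 2 puts the final contact at 180 days (165 to 195 allowed).

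Protocol 6.5 sets what must go into the eCRF. The general rule is "All concomitant medications/products/vaccines, except vitamins and dietary supplements, administered during the 30-day period following vaccination (Day 1 to Day 31". Other bullets reach past Day 31. One covers Shingrix "or any AS01-containing vaccine throughout the entire study". Two more carry no Day 31 limit: vaccines relevant to a reportable SAE or pIMD, and vaccines leading to non-eligibility or to elimination from the analysis. COVID-19 vaccines are not named.

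The same section has participants asked about vaccinations at every visit and contact. Protocol Table 1 marks concomitant vaccination for eCRF documentation at Visit 1, Visit 2 and Month 6, and refers to 6.5 for details.

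For participants with no report, SAP 5.2.2.1.2 says: "Participants who did not report an event or concomitant medication will be considered as participants without the event or the concomitant medication".

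SAP 5.5 also summarises "The overall incidence of COVID-19 AEs and SAEs" without a time window, and adds: "The incidence of these events at individual PT level can be obtained from the standard AE/SAE summaries".

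**The concern.** The table promises a description over the whole study, while the general recording rule covers its first month. A participant vaccinated against COVID-19 at, say, Day 60, with no related SAE or pIMD, may leave no entry in the eCRF. If the SAP rule for non-reporters is applied, that participant counts as not vaccinated.

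A COVID-19 vaccine is another immunological exposure during the period in which SAEs and pIMDs are followed to Month 6. A reader of the report or the public posting would use this table to judge how common that exposure was. A percentage drawn mainly from the first month, labelled as the whole study and given an exact confidence interval, would look precise while missing later vaccinations. The Clopper-Pearson interval reflects sampling error only and would not show the gap.

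**Working it through.** The documents give no COVID-19 vaccination figure, so there is nothing to reproduce. The check compares the recording rules with the table and then sizes the possible gap.

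**1. Recording rules by period**

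| Period | Rule | COVID-19 vaccine covered? |
|---|---|---|
| Before Dose 3 | Protocol 8.2.1.2 and Table 1: vaccination history since the parent study, taken at Visit 1 | Yes |
| Day 1 to Day 31 | Protocol 6.5, general rule | Yes |
| After Day 31 to Month 6 | Protocol 6.5, remaining bullets only | Not clearly |

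**2. A routine COVID-19 vaccine at Day 60, no SAE or pIMD.** If it is not AS01-containing, the Shingrix/AS01 bullet does not apply. The SAE/pIMD bullet does not apply. Elimination is unlikely to apply: Day 60 is beyond the 30-day restriction in Protocol 5.2.2, and the last blood sample is at Visit 2 (30 to 42 days after the dose). The one open route is a vaccine classed as non-registered under Protocol 5.2.2, which the documents do not settle.

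**3. Does the Month 6 mark in Table 1 close the gap?** It points to 6.5 for scope. If 6.5 already meant all vaccines to Month 6, its separate bullet extending Shingrix/AS01 recording to the entire study would be redundant for vaccines. The text therefore leans towards limited recording at Month 6, without being explicit.

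**4. Share of follow-up outside the general window** = (T − 30)/T, with T the day of the final contact:
- T = 165: 135/165 = 81.8%
- T = 180: 150/180 = 83.3%
- T = 195: 165/195 = 84.6%

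**5. Illustration of the effect on the table.** Let p be the true percentage vaccinated in-study, f the fraction of those vaccinations falling in Day 1 to Day 31, and g the fraction of later ones recorded anyway. The reported percentage is p × [f + g(1 − f)]. The values of p, f and g are assumptions. N = 300 comes from three groups of about 100 (Protocol Table 4).

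With even timing (f = 30/180) and none of the later ones recorded (g = 0):

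| True p | Reported (95% CI) | With full recording (95% CI) |
|---|---|---|
| 20% | 10/300 = 3.3% (1.6 to 6.0) | 60/300 = 20.0% (15.6 to 25.0) |
| 50% | 25/300 = 8.3% (5.5 to 12.1) | 150/300 = 50.0% (44.2 to 55.8) |
| 80% | 40/300 = 13.3% (9.7 to 17.7) | 240/300 = 80.0% (75.0 to 84.4) |

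With p = 50% and g = 0, changing the timing gives:
- f = 0: 0/300 = 0%
- f = 0.05: 8/300 = 2.7%
- f = 0.5: 75/300 = 25.0%
- f = 1: 150/300 = 50.0%, no loss

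With p = 50% and even timing, if half of the later vaccinations are recorded anyway (g = 0.5): 50% × [1/6 + 0.5 × 5/6] = 50% × 7/12 = 29.2%.

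Protocol 5.2.2 restricts other vaccines from 30 days before to 30 days after the dose, reducible for emergency mass vaccination. This makes f below 1/6 plausible.

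**The case against.** The strongest reply is that Month 6 recording is in the protocol. Table 1 carries the eCRF mark at that contact, participants are asked about vaccinations there, and the eCRF itself is not available to inspect. Sites may well have entered every vaccine. This stands to the extent that non-capture cannot be asserted. It does not remove the gap, because the mark takes its scope from 6.5.

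Second, a COVID-19 vaccine relevant to a late SAE or pIMD is recorded whatever the day, which covers the case that matters most for safety. That stands, but it does not give the percentage of participants exposed, which is what SAP 5.5 tabulates.

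Third, the rule for non-reporters is worded for events and concomitant medication. Applying it to vaccines is plausible rather than stated. SAP 5.5 offers no other rule.

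Fourth, all analyses are descriptive (SAP 6). That limits the importance of the point and is accepted.

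Two stronger readings are tempting and are not supported. A reader might infer that nothing after Day 31 is recorded; the 6.5 exceptions and the Month 6 mark contradict that. A reader might also infer that the COVID-19 AE summary will make COVID-19 look more often serious than it was, since all AEs are collected for 30 days ("All AEs that occur during 30 days following administration of the dose of study vaccine (Day 1 to Day 31) must be recorded") and SAEs to Month 6. SAP 5.5 plans no serious-to-all ratio and points to the standard AE and SAE summaries, which have their own windows (30 days in SAP 5.2.1.1, entire study in SAP 5.3.1.3). Unlabelled windows there call for clarification and do not show a bias.

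**Conclusion.** The point holds as a mismatch between a planned table and the data the protocol clearly requires. Followed as written, the plan is likely to report too low a percentage for COVID-19 vaccination during the study. The part before the study is sound.

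About 83% of nominal follow-up (82% to 85% over the allowed contact window) lies outside the general recording rule. That is a share of time. It equals the share of vaccinations missed only if they were spread evenly and none after Day 31 was entered. The documents give neither the timing nor the actual entries, so the undercount could run from none to nearly all in-study vaccinations.

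No primary or secondary endpoint, and no analysis set, depends on the table. It is worth correcting because the fix is cheap and the end-of-study analysis goes to the study report and public posting (SAP 7.1).

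**What to change.** Preferred: reconcile Protocol Table 1 with 6.5 by stating that COVID-19 vaccines are recorded up to the Month 6 contact, as is already done for Shingrix and AS01-containing vaccines. The contact and the question exist, so the added burden is an eCRF entry. The cost is a small protocol change. Protocol 10.1.1 requires IEC/IRB approval of amendments before changes to the study design are implemented, and the change may come too late for participants already followed up. The documents do not show how many were still in follow-up when SAP 5.5 was added.

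Otherwise: restrict the SAP 5.5 table and relabel it as before Dose 3 and up to Day 31. This needs SAP wording only, but gives up the description of exposure between Day 31 and Month 6. If the completed eCRFs show that later vaccinations were entered, the SAP could keep the longer period and say what the recording rested on.

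In either case, state the denominator and how a participant with no vaccination entry is counted.

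As a secondary clarification, label each COVID-19 AE row with its collection window: all AEs and severe AEs to Day 31; SAEs and AEs leading to withdrawal to Month 6. This is also SAP wording only.

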6. ANALYSIS INTERPRETATION

All analyses are descriptive.

7. INTERIM ANALYSES

7.1. Sequence of analyses

The analyses will be performed stepwise:

- A first analysis will be performed when all data as clean as possible are available for at least primary and secondary endpoints up to Visit 2 (Day 31).
- The final end-of-study analysis will be performed when all data for at least primary and secondary endpoints up to study conclusion (Month 6) are available. All available tertiary endpoints will also be analyzed in this step. Individual listings will only be provided at this stage.

If data for tertiary endpoints become available at a later stage, (an) additional analysis/analyses will be performed.

Description	Analysis ID	Disclosure Purpose (CTRS=public posting, SR=study report, internal)
End of study analysis	E1_01	CTRS, SR
Analysis up to Day 31	E1_02	CTRS

7.2. Statistical considerations for interim analyses

All analyses will be conducted on final data (as clean as possible) and therefore no statistical adjustment for interim analyses is required.

8. CHANGES TO THE PROTOCOL DEFINED STATISTICAL ANALYSIS

N/A

9. NON-STANDARD DATA DERIVATION RULES AND STATISTICAL METHODS

The following sections describe additional derivation rules and statistical methods which are not presented in section 10.1 (Business rules for standard data derivations and statistical methods).

9.1. Handling of missing data

9.1.1. Dates

When partially completed dates (i.e. with missing day or month) are used in calculations, the following rules will be applied:

- Adverse event start dates with missing day:
 - If the month is not the same as the vaccine dose, then the imputed start date will be the 1st of the month
 - If the event starts in the same month as the vaccine dose, the flag indicating if the event occurred before or after vaccination (AE.AESTRTPT) will be used to complete the date. If ‘after vaccination’ is selected, the imputed start date will match the vaccine dose given during that month. If ‘before vaccination’ is selected, the imputed date will be one day before the vaccine dose given during that month.
- Adverse event start dates with missing day and month:
 - If the year is not the same as the vaccine dose, then the imputed start date will be the 1st of January.
 - If the event starts in the same year as the vaccine dose, the flag indicating if the event occurred before or after vaccination (AE.AESTRTPT) will be used to complete the date. If ‘after vaccination’ is selected, the imputed start date will match the first vaccine dose given during that year. If ‘before vaccination’ is selected, the imputed date will be one day before the first vaccine dose given during that year.
 - Adverse event end dates with missing day: the imputed end date will be the last day of the month (30 or 31) or the study conclusion date whichever comes first.
 - Adverse event end dates with missing day and month: the imputed end date will be the last day of the year (31st of December) or the study conclusion date whichever comes first.

All other cases of incomplete AE or concomitant medication/vaccination start date will follow the standard rules above.

10. ANNEXES

10.1. Business rules for standard data derivations and statistical methods

This section contains standard rules for data display and derivation for clinical and epidemiological studies.

10.1.1. Attributing events to vaccine doses

The dose relative to an event is the most recent study dose given to a participant prior to the start of a given event. For example, if the start date of an adverse event is between Dose 1 and Dose 2, the relative dose will be Dose 1.

If an event starts on the same day as a study dose, the relative dose will be derived from the additional information provided in the case report form (CRF) using the contents of the flag indicating if the event occurred before or after study dose. If 'after study dose' is selected, the relative dose for the event will be the one administered on the start day of the event. If 'before study dose' is selected, the relative dose for the event will be the dose prior to this one.

10.1.2. Handling of missing data

10.1.2.1. Dates

When partially completed dates (i.e. dates missing a day and/or month) are used in calculations, the following standard rules will be applied:

- A missing day will be replaced by 15
- A missing day and month will be replaced by June 30th.

See also exceptions in section [9.1.1](#).

10.1.2.2. Laboratory data

Missing laboratory results (including immunological data) will not be replaced.

10.1.2.3. Daily recording of solicited events

10.1.2.3.1. Studies with paper diaries

For studies using paper diaries which have questions in the CRF indicating the presence or absence of solicited events, the following rules are applicable:

- Denominators for the summary of administration site (or systemic) solicited events will be calculated using the number of participants who respond "Yes" or "No" to the question concerning the occurrence of administration site (or systemic) events.

- When a specific solicited event is marked as having not occurred following a specific study dose (i.e. SDTM CE.CEOCCUR=N for the specified post-dose period for the event in question), all daily measurements will be imputed as Grade 0.
- When a specific solicited event is marked as having occurred following a specific study dose (i.e. SDTM CE.CEOCCUR=Y for the specified post-dose period for the event in question), any missing daily recordings will be given imputed values to allow them to contribute to the ‘Any’ rows but not to specific grade rows of the solicited event summary tables.

The following table shows how participants contribute to each category for a specific solicited event over the Day X to Day Y post-dose period:

Solicited event category	Participants included in the calculation of the numerator
Any	All participants with at least one occurrence of the adverse event at grade 1, grade 2, or grade 3 between Day X and Day Y or with the adverse event marked as present and at least one missing daily recording between Day X and Day Y
At least grade 1	All participants with at least one occurrence of the adverse event at grade 1, grade 2, or grade 3 between Day X and Day Y
At least grade 2	All participants with at least one occurrence of the adverse event at grade 2 or grade 3 between Day X and Day Y
At least grade 3	All participants with at least one occurrence of the adverse event at grade 3 between Day X and Day Y

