9.4.1.3. Reactogenicity/Safety

- For a given participant and the analysis of solicited events within 4 days post-vaccination, missing or non-evaluable measurements will not be replaced. Therefore, the analysis of solicited events will include only vaccinated participants with documented solicited safety data (i.e., paper diary completed).
- For analysis of unsolicited AEs, SAEs, pIMDs and concomitant medications, all vaccinated participants will be considered. Participants who did not report an event or concomitant medication will be considered as participants without the event or the concomitant medication, respectively.

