10.3.3. Solicited events**a. Solicited administration site events**

The following administration site events will be solicited:

Table 14 Solicited administration site events

Pain at the injection site
Erythema at the injection site
Swelling at the injection site

CONFIDENTIAL213569 (RSV OA=ADJ-011 EXT:002 MTH20)
Protocol Amendment 1 Final**b. Solicited systemic events**

The following systemic events will be solicited:

Table 15 Solicited systemic events

Fever

Note: participants will be instructed to measure and record the oral body temperature in the evening. Should additional temperature measurements be performed at other times of day, participants will be instructed to record the highest temperature in the diary card.

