5.2. Primary endpoint(s)

5.2.1. Analysis planned in the protocol

5.2.1.1. Safety analysis

The safety analysis will be performed on the ES for all participants.

A descriptive analysis by group and overall will present a summary of:

- The number and percentage of participants with at least one administration site event (solicited and unsolicited), with at least one systemic event (solicited and unsolicited) and with any AE during the 4-day or 30-day follow-up period will be tabulated with exact 95% CI after Dose 3. The same computations will be done for Grade 3 AEs, Grade 3 non-serious AEs, related AEs and AEs resulting in a medically attended visit.
- The number and percentage of participants reporting each individual solicited administration site event (any grade, Grade 3, with medically attended visit) and solicited systemic event (any grade, Grade 3, with medically attended visit) during the 4-day follow-up period (i.e., on the day of vaccination and 3 subsequent days) will be tabulated for each group after Dose 3.
- For fever, the number and percentage of participants reporting fever by half degree ($^{\circ}\text{C}$) cumulative increments during the 4-day follow-up period (i.e., on the day of vaccination and 3 subsequent days) will be tabulated for each group after Dose 3.
- The number and percentage of participants with any unsolicited AEs during the 30-day follow-up period (i.e., on the day of vaccination and 29 subsequent days) with its exact 95% CI will be tabulated by group and by Medical Dictionary for Regulatory Activities (MedDRA) preferred term. The same tabulation will be done for Grade 3 unsolicited AEs, for any causally related unsolicited AEs, for Grade 3 causally related unsolicited AEs and for unsolicited AEs resulting in a medically attended visit. The verbatim reports of unsolicited AEs will be reviewed by a qualified person and the signs and symptoms will be coded according to the MedDRA Dictionary for Adverse Reaction Terminology. Every verbatim term will be matched with the appropriate Preferred Term.
- The number and percentage of participants with at least one report of SAE/pIMD classified by the MedDRA Preferred Terms and reported during the 30-day follow-up period (i.e., on the day of vaccination and 29 subsequent days) will be tabulated with exact 95% CI. The same tabulation will be done for related SAEs/pIMDs. SAEs/pIMDs will also be described in detail.

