5.2.2. Additional considerations

5.2.2.1. Safety analysis

5.2.2.1.1. Solicited Events

Solicited events will be reported daily during the 4-day (from Day 1 to Day 4) follow up period after vaccination, using structured diaries. Missing or non-evaluable measurements will not be replaced. Therefore, the analysis of solicited events will include only vaccinated participants with documented solicited safety data (i.e., paper diary completed).

In order to summarize the data, the maximum intensity of local injection site erythema/swelling (in mm) and fever (in °C) will be categorized as follows:

Grading	Erythema/swelling	Fever
0:	≤ 20 mm	< 38.0°C (100.4°F)
1:	> 20 - ≤ 50 mm	≥ 38.0°C (100.4°F) - ≤ 38.5°C (101.3°F)
2:	> 50 - ≤ 100 mm	> 38.5°C (101.3°F) - ≤ 39.0°C (102.2°F)
3:	> 100 mm	> 39.0°C (102.2°F)

Fever is defined as temperature ≥ 38.0°C / 100.4°F (regardless of the location of measurement). The preferred location for measuring temperature in this study will be the oral cavity. Body temperature will also be summarized by 0.5°C increments as follows: ≥38.0, >38.5, >39.0, >39.5, >40.0 °C.

Each participant’s data will be summarized according to the maximal severity observed during the follow-up period for each event, followed by a summary across participants.

- Compliance in completing solicited events information will be tabulated.
- The number of days with solicited events reported during the 4-day follow-up period will be tabulated for each solicited event, using descriptive statistics (mean, min, Q1, median, Q3, maximum). The same tabulation will be done for Grade 3 solicited events.
- The prevalence of each solicited event (any grade and grade 3) will also be represented graphically per group.

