5.2.2.1.3. Combined Solicited and Unsolicited Adverse Events

A summary of participants with all combined solicited (regardless of their duration) and unsolicited adverse events will be provided. Solicited events will be coded by MedDRA as per the following codes

Solicited symptom	Lower level term code	Corresponding Lower level term decode
Pain	10022086	Injection site pain
Erythema	10015150	Erythema
Swelling	10053425	Injection site swelling
Fever	10016558	Pyrexia

For clinicaltrials.gov and EudraCT posting purposes, a summary of combined solicited and unsolicited non-serious adverse events will be produced by System Organ Class and preferred terms and according to occurrence of each event.

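### Does the paper-diary rule in the SAP undercount solicited events when a specific item is left blank after a group-level 'Yes'?

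*SAP*

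**What the plan says.** SAP section 10.1.2.3.1 governs solicited events collected on paper diaries.

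- **Denominator.** "Denominators for the summary of administration site (or systemic) solicited events will be calculated using the number of participants who respond"; that is, everyone who gives either answer at group level. It does not depend on the answers for individual events.
- **Specific event marked N.** "When a specific solicited event is marked as having not occurred following a specific study dose", every daily value is set to Grade 0.
- **Specific event marked Y.** Missing days count towards 'Any' but towards no grade row.
- **Numerator for 'Any'.** A recorded day at Grade 1 to 3, "or with the adverse event marked as present and at least one missing daily recording between Day X and Day Y".

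Three other places bear on the point.

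- Protocol section 10.3.3 lists pain, erythema and swelling as the solicited administration site events. Under "The following systemic events will be solicited" it lists fever alone. The table in SAP section 5.2.2.1.3 ("Solicited events will be coded by MedDRA as per the following codes") has the same four events.
- SAP section 5.2.1.1 also tabulates participants with "at least one administration site event (solicited and unsolicited" combined).
- SAP section 5.2.2.1.1 states: "Missing or non-evaluable measurements will not be replaced". Protocol section 9.4.1.3 says the same. Both then restrict the solicited-event analysis to vaccinated participants with a completed paper diary.

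**The concern.** The three bullets and the numerator table do not name one possible data state: the group question answered 'Yes', with the specific item answered neither Y nor N. If that participant also has a missing day and no recorded Grade 1 or higher value, both routes into 'Any' are closed, yet the participant remains in the denominator. The tabulated result is the same as for a marked 'N', an answer the participant never gave.

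Fever makes the point most sharply. With only one solicited systemic event, a 'Yes' to the systemic question appears to mean fever, but the table would show no fever. For the three local events, someone who answered 'Yes' and completed none of the items would be shown as free of all three. The SAP also does not say whether a group 'Yes' by itself counts in the row for at least one administration site event.

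Occurrence of solicited events is a primary endpoint, and the error would run towards understating reactogenicity. One could also argue that counting a blank as absent amounts to replacing a missing value, contrary to SAP section 5.2.2.1.1.

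**Working it through.** The plan states no figure to reproduce: protocol section 9.1 has no hypotheses and section 9.2 no sample size calculation. The check is first of the logic, then of the possible size.

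**Step 1. Apply the rules of SAP 10.1.2.3.1 to a participant with group answer 'Yes'.**

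| Specific item | Daily record | In denominator | In 'Any' |
|---|---|---|---|
| Y | all days missing | yes | yes |
| Y | Grade 0 and missing | yes | yes |
| Y | all days Grade 0 | yes | no |
| N | any (set to Grade 0) | yes | no |
| blank | at least one day Grade 1 or higher | yes | yes |
| blank | all days Grade 0 | yes | no |
| blank | all days missing | yes | no |
| blank | Grade 0 and missing | yes | no |

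Only the last two rows are in question. A blank item with a graded day is counted as an event. A blank item with four recorded Grade 0 days is properly a non-event.

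**Step 2. Bound the error.** Let n be the denominator, k the participants with the event under the rules as written, and m the participants in the last two rows. The reported rate is k/n. If a number j of the m truly had the event, the rate is (k + j)/n with 0 ≤ j ≤ m, so the shortfall lies between 0 and m/n. For fever, j need not equal m. Fever is a measured temperature of at least 38.0°C (protocol section 10.3.8.1), and a 'Yes' with no qualifying temperature could be fever, a lower temperature, another symptom or a transcription error.

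With n about 100 per group (protocol Table 4), one participant is at most 1/100 = 1.0 percentage point. Over three groups, n is about 300 and one participant is at most 1/300 = 0.33 points.

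**Step 3. Illustrate.** The documents give neither k nor m, so both are assumed. Intervals are exact 95% (Clopper-Pearson, SAP section 10.1.5.1).

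Fever, k = 2, n = 100. As written: 2/100 = 2.0% (0.2 to 7.0).

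| m | All m counted | All m removed from denominator |
|---|---|---|
| 1 | 3/100 = 3.0% (0.6 to 8.5) | 2/99 = 2.0% (0.2 to 7.1) |
| 2 | 4/100 = 4.0% (1.1 to 9.9) | 2/98 = 2.0% (0.2 to 7.2) |
| 3 | 5/100 = 5.0% (1.6 to 11.3) | 2/97 = 2.1% (0.3 to 7.3) |

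Erythema, k = 10, n = 100. As written: 10/100 = 10.0% (4.9 to 17.6).

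| m | All m counted | All m removed from denominator |
|---|---|---|
| 1 | 11/100 = 11.0% (5.6 to 18.8) | 10/99 = 10.1% (5.0 to 17.8) |
| 3 | 13/100 = 13.0% (7.1 to 21.2) | 10/97 = 10.3% (5.1 to 18.1) |
| 5 | 15/100 = 15.0% (8.6 to 23.5) | 10/95 = 10.5% (5.2 to 18.5) |

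Removing the unanswered participants barely moves the estimate. Counting all of them moves it by m points. In every row the interval overlaps heavily with the one obtained as written.

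**Step 4. Ask whether m is likely to be above zero.** Completed diary cards are collected and verified with the participant at Visit 2, and missing cards are chased (protocol section 10.3.7). Site staff transcribe them into the eCRF, and monitors verify source data (section 10.1.7). SAP section 5.2.2.1.1 tabulates compliance in completing the solicited-event information. A group 'Yes' with no specific answer is an obvious inconsistency that these steps would ordinarily raise as a query.

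**The case for a change.** The best case for acting is that the gap is real on the current text, touches a primary endpoint, leans towards understating reactogenicity, and could be closed in one line. Fever may be uncommon, so a single case matters: if two in 100 have recorded fever, one lost report turns 3.0% into 2.0%. Protocol section 8 also lets diaries travel by mail or electronically in special circumstances, which could weaken verification. The first SAP version (1 December 2020) had a bullet for this very answer pattern, so the sponsor evidently thought it possible.

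Part of this stands. The data state is not named, and the literal result is as described. The rest is weaker.

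- The fever argument needs separate systemic and fever items, with the second able to stay blank after a 'Yes' to the first. The SAP wording hints at this, but the eCRF is not available. If they are one item, or an edit check links them, 'Yes' marks fever present and the existing Y rule applies.
- A difference from superseded text is not an error. The change in Amendment 1 fits a state that cannot occur, or a choice not to turn one group 'Yes' into pain, erythema and swelling together, as well as it fits an oversight.
- The text does yield an answer: in the denominator, not in 'Any'. Reporting k/(n − m) would override an explicit denominator rule, so two programmers are unlikely to diverge on that ground.
- The clash with the no-replacement sentence is slight. Leaving a blank out of the numerator assigns it no grade, and that sentence is followed by a participant-level restriction to completed diaries; it sets no event-level denominators.
- Remote transmission of diaries does not remove transcription or source verification.

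**Conclusion.** The observation is correct, but it is missing detail about a rare data state and not a flaw in the analysis. If the eCRF permits a blank specific item after a group 'Yes', and the participant also has a missing day and no graded day, the rate for that event may be low by 0 to m participants: up to 1.0 percentage point each in a group of about 100, or 0.33 points overall. The number affected is unknown and may be zero.

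This conclusion rests on two assumptions: that the usual diary verification and queries leave few such blanks, and that any that remain would be seen and handled sensibly when the data are cleaned. Both are reasonable given the procedures in the protocol. The safety analyses estimate proportions with exact intervals and test nothing (SAP section 6), so a shift of this size would leave the descriptive conclusions as they are. The team could confirm that the eCRF forces an answer to each specific item, but the plan does not depend on it and no change is called for.
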